### **Psychophysiological Data Collection**

Participants may experience mild discomfort or distress during the psychophysiological assessment in response to being in the booth during the session which involves periods of light and dark. Procedures will be explained fully and participants will be instructed to end the session at any time if they feel any discomfort or stress.

### **Heart Rate Variability Data Collection**

IRB Protocol Version 12

11/23/20

Participants may experience redness or itching at the site where the electrodes for the Bodyguard are placed (clavicle and ribcage). These risks are unlikely, and if they occur, should resolve within a few days.

### **Electrocardiogram**

Participants may experience temporary irritation/discomfort from the ECG electrodes on the skin.

### **Loss of Confidentiality**

In order to protect against the risk of a breach in confidentiality, study data will be stored in locked filing cabinets within a locked research office that can only be accessed by research personnel. No names or identifying information will be used in publications that result from this study. Identifying information will not be released to any outside party (beyond those connected to the study) without written consent from the participant. An electronic dataset that includes identifiers linked to the subject identification code will be stored in a password-protected database that is located on a secure LAN within our locked research suite. Hard copies of forms that include identifiers (e.g., signed informed consent forms) will be kept in a secure, locked file cabinet within a locked VA research office.

## **D. BENEFITS**

There are potential benefits to participants. Trauma Center-Trauma Sensitive Yoga and Cognitive Processing Therapy-Cognitive are both treatments that have the potential to improve PTSD symptoms, sleep, and pain. They will be exposed to a therapeutic activity that they can continue outside of sessions if they choose. Participants will also be offered the intervention to which they were not randomly assigned following their completion of the study intervention and data collection, e.g. those assigned to CPT will be offered Trauma Center-Trauma Sensitive Yoga after completion of the study. Participants in this study will be involved in a process that may provide future benefit to other MST-exposed female Veterans with PTSD. The potential benefits to others include knowledge development necessary to implement this intervention throughout the VA if it is successful in treating PTSD, chronic pain and insomnia in female Veteran sexual assault survivors.

The knowledge to be gained in this study is scientifically essential to determine the effectiveness of the experimental intervention. This study has the potential to impact PTSD treatment at the national level of the VA, which is the largest health care system in the United States. This RCT could yield meaningful data to support clinical guidelines for a complementary and alternative medicine intervention which could be disseminated to and implemented in VA Medical Centers nationwide, and thus improve the quality of care for female Veterans with PTSD.

## **E. DATA MONITORING AND ANALYSIS**

### **Data Management**

As part of this protocol, we will collect data via chart review, self-report form, interview-based assessment, blood collection, heart-rate variability device, ECG report, polysomnogram and dark-enhanced startle testing (Atlanta only). Data will either be collected at the AVAMC Clinical Studies Center or the Trauma Recovery Program or Portland VA or Vancouver, WA VA location of the VAPORHCS and then subsequently transported back to respective VAMC for storage. Any sensitive data including consent forms, session sign-in sheets etc. will be transported in a blue lock-bag as outlined in the approved VA Research Data Inventory (Privacy and Data Security Section). Data will be captured, stored and processed in the following ways:

### **Chart Review**

Data will be extracted from the VA medical record including diagnoses, active medications, and reportable adverse events (if applicable). These data will be added to the VA REDCap database.

**Self-Report and Interview Data:** Self-report and interview data will be captured through pen and paper measures or through direct data entry into the VA REDCap (Research Electronic Data Capture) project database using a VA-approved tablet. REDCap is a secure, web-based application designed to support data capture for research studies. REDCap for VA is installed and accessible only behind the VA firewall and data is backed-up nightly and every 6 hours. In addition, VA REDCap provides data de-identification features and

restricts access to PHI at the user-level. Deidentified self-report and interview data will be securely exported from VA REDCap to Excel or SPSS and then uploaded to the VA password-protected research drive for analysis as needed. Periodically, deidentified self-report and interview data will be submitted to the study statistician for data analysis and review.

Additionally, demographic information, including identifiers (study ID), for each participant will be stored in the REDCap database that is password-protected and accessible only by approved members of the research team. The research suite is locked at all times with access granted only to authorized personnel. Data residing on VA desktop computers are routinely backed up on a secure, off-site server. Thus, all data are protected from loss and are stored devoid of all patient identifiers.

**Cytokine Data:** In Atlanta, blood samples will be collected by trained study staff or CSC staff in the Atlanta VA Clinical Studies Center and labelled with date, study ID, and visit number only. Initial sample processing will take place in the CSC lab by trained staff before being sent to another lab within the VA for final analysis. Any sample remaining after initial analysis will be stored until the end of the study at which point remaining specimen will be destroyed. Deidentified cytokine data will be sent from the lab to the project manager. These data will be stored on the secure VA research server and the VA REDCap database until being sent to the Emory statistician for analysis. In Portland, blood samples will be collected by trained study staff in the VAPORHCS and labelled with date, study ID and visit number only. Initial sample processing will take place in the [name] Lab at the VAPORHCS prior to shipment to the CSC of the AVAHCs for analysis. Any sample remaining after initial processing will be stored until the end of the study at which point remaining specimens will be destroyed.

**Heart Rate Variability (HRV) Data: At both sites,** HRV data will be captured using the portable Bodyguard device which participants will wear for up to 48 hours. In Atlanta, once the device is returned to study staff, deidentified HRV data from the USB device will be downloaded to either an Emory laptop or VA computer that belongs to the PI and contains data analysis software. The data will then be analyzed by trained study staff and exported to Excel. Periodically, the data will be retrieved from the laptop and uploaded to Box.net. [name] (Cardiologist/Co-Investigator) will assist the study staff with troubleshooting any issues and address any questions that arise during the data analysis process. [name] will process the de-identified HRV data on his Emory workstation for generation of heart rate variability metrics. Data, although de-identified, will be transferred via HIPAA compliant methods, including encrypted VA-issued USB flash drive, and Box.net.

In Portland, HRV data will be captured using the portable Bodyguard device which participants will wear for up to 48 hours. Once the device is returned to study staff, fully de-identified HRV data from the USB device will be downloaded to a VA computer and saved on the secured research folder designated for this study (\R01PORHSM03.r01.med.va.gov\Research\[name] Research\Project Stress Less II) to which [name] will have access for the purpose of data analysis.

**Electrocardiogram Data:** In Atlanta, 12-Lead ECGs will be completed by trained study staff using an IRB approved ECG machine. Paper ECG reports coded with the SID will be printed, stored in the participant binder and scanned to the secure VA research server where they will be reviewed periodically by [name] (Cardiologist/Co-Investigator). These reports will contain the subject identification number and time-point, but no protected health information. Periodically, these data will be saved to a VA-issued USB drive and uploaded to the secure research drive and VA REDCap database. [name] will process the de-identified ECG data on his Emory workstation for generation of repolarization metrics. Data, although de-identified, will be transferred via HIPAA compliant methods, including encrypted VA-issued USB flash drive, and Box.net.

In Portland, 12-Lead ECGs will be completed by trained study staff using an IRB approved ECG machine. Paper ECG reports coded with the SID will be printed, stored in the participant binder and scanned to the secure VA research server. These reports will contain the subject identification number and time-point, but

no protected health information. The PI will have access to these original data to provide to [name] (cardiologist/CO-Investigator) for analysis.

### **Polysomnogram Data (Atlanta Only)**

Polysomnogram results will be extracted from the VA medical record, recorded onto a form, and entered into the VA REDCap database.

### **Psychophysiological Data (Dark-Enhanced Startle [Atlanta Only])**

Psychophysiological data will be captured on a laptop containing Biopac software. These deidentified data will be analyzed using Mindware software and then exported to Excel. These data will be stored on the VA research drive.

### **Data Quality**

All data will be examined for completeness and an assessment of missing data will be performed to check for any biases which may occur. Data will be monitored and entered promptly in order to detect issues as they arise. Special attention will be paid to note what, if any, demographic and clinical factors may be related to subject attrition, retention and adherence. Study retention refers to those who complete all study-related assessments. Dose-effects will be accounted for based on the number of treatment sessions attended by each subject relative to their assigned group. Analyses will be performed to determine what if any covariates may be predictive of missing data over time and these variables will be adjusted for in subsequent models. Close attention will be paid to underlying normality assumptions. Numerical transformations (such as square root, log, and inverse functions) may be applied to correct for deviations due to skewness.

### **Power Analysis**

Given the estimated final sample size of 104 (52 per group) after expected levels of attrition (50% attrition from 210), we will be powered at 80% to detect moderate effect sizes for any differences between the groups (two-group independent t-tests effect size (Cohen's d) of 0.555 and chi-square tests for differences in proportions between the two-groups effect size (Cohen's omega,  $\omega$ ) 0.274 and higher) as well as moderate-to-large effect sizes detected for differences between the groups over time (repeated measures group-by-time interaction effects: effect size of 0.28, Cohen's f) will be detected. Power analyses will be completed using PASS v.13.0.8.

### **Statistical Analysis**

Comparisons between the groups at baseline will be run using t-tests, Mann Whitney non-parametric tests, and chi-square tests as appropriate. However, when numerical transformations are not sufficient, non-parametric and generalized non-normal response functions may also be employed. Multilevel mixed models (MLM) will be used instead of repeated-measures analysis of variance (RM-ANOVA), to analyze the differences between the groups over time. As opposed to RM-ANOVA which assumes independence between time points and assumes complete data for all subjects at all time-points, MLM adjusts for attrition (missing data) over time and applies appropriate correlation structure between the time points. Multilevel modeling also provides insight into the variance components of the outcomes relative to those related to within-subject variability over time and those related to between-subject differences. These variance components are important for understanding the utility of each measure relative to reliably assessing each outcome. Generalized functions of these MLM models may also be run for non-normal outcomes due to highly skewed or zero-inflated data (common with biomarker and some behavioral measures) or binary outcomes (e.g. diagnosis determinations). These statistical modeling approaches will be applied appropriately to the outcome measures of interest for each of the three research aims. SPSS Version 22.0 will be used for all statistical analyses.

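### The group-by-time analysis names no adjustment for the baseline outcome and, read naturally, leaves unused the equality of baseline means that randomisation guarantees

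*Combined protocol and SAP*

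**What the plan says.** Statistical Analysis (section E) states: "Multilevel mixed models (MLM) will be used instead of repeated-measures analysis of variance (RM-ANOVA"), with the purpose "to analyze the differences between the groups over time". It gives baseline one role: "Comparisons between the groups at baseline will be run using t-tests, Mann Whitney non-parametric tests, and chi-square tests as appropriate". Power Analysis takes an "estimated final sample size of 104 (52 per group") after "50% attrition from 210", and claims "we will be powered at 80"% for "two-group independent t-tests effect size (Cohen's d) of 0.555" and for "repeated measures group-by-time interaction effects: effect size of 0.28, Cohen's f".

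Data Quality provides for adjustment only for covariates found to predict missing data; the baseline outcome is neither named nor excluded. Table 1 schedules CAPS-5, PCL-5, BPI, PSQI, VR-12 and the PROMIS measures at Time 1 and at Times 2 to 4, and its footnote b places randomisation after all other baseline procedures. The post hoc equivalence section compares unadjusted changes from baseline.

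No section writes out the fixed effects, says whether the arms' baseline means are free or common, or gives a correlation between baseline and follow-up.

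**The concern.** A group-by-time interaction tests whether treatment works only if baseline is one of the levels of time. Fitted to Times 2 to 4 alone, it tests whether the arm difference changes between follow-up visits, and a constant benefit would give no interaction. Together with the absence of any named baseline covariate or common baseline mean, this makes the free-baseline model the natural reading.

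In that model, with complete data, the arm contrast at a visit is the difference in change from baseline. It estimates a baseline difference between arms that is known to be zero in expectation, because baseline is measured before randomisation. Removing that parameter, or conditioning on the baseline value, gives a contrast at least as precise from the same data. At stake is the width of the intervals for the continuous outcomes under all three aims, in a trial that expects to lose half its sample.

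**Working it through.** **Inputs.** From Power Analysis: 52 per arm, d = 0.555 and 80% power. Alpha is not stated there; two-sided 5% is assumed because it reproduces the stated power (one-sided 5% gives 87.8%). The correlation between baseline and follow-up (rho) and the ratio of baseline SD to follow-up SD (k) are not given. I use rho = 0.3, 0.5 and 0.7, with k = 1 unless stated.

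**Step 1: the plan's figure.** Noncentral t with noncentrality 0.555 × √(52/2) = 2.83 and 102 df gives 80.0%. The plan's figure reproduces.

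**Step 2: variance of one follow-up contrast**, relative to using follow-up alone:
- Free baseline means (difference in change): 1 + k² − 2·rho·k, which is 2(1 − rho) at k = 1.
- Baseline-adjusted (common mean or covariate): 1 − rho².
- Difference between the two: (k − rho)², which is never negative.

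Power comes from d divided by the square root of the factor, with 102 df (101 for the adjusted contrast).

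**Step 3: complete data, equal SDs, 52 per arm.**

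| rho | Factor, free | Factor, adjusted | Power, free | Power, adjusted | Gain (points) |
|---|---|---|---|---|---|
| 0.3 | 1.40 | 0.91 | 65.9% | 83.6% | 17.7 |
| 0.5 | 1.00 | 0.75 | 80.0% | 89.9% | 9.9 |
| 0.7 | 0.60 | 0.51 | 95.1% | 97.5% | 2.4 |

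A simulation at rho 0.5 gave 79.8% and 89.5%.

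**Step 4: dropouts' baselines kept.** Suppose all 210 are randomised (an assumption), so that 105 per arm have a baseline and 52 per arm a follow-up, with dropouts missing at random. The free-baseline variance per arm is proportional to (1 − rho)²/105 + (1 − rho²)/52. Multiplying by 52 gives the factor:
- rho 0.3: 0.495 × 0.49 + 0.91 = 1.153, power 74.2% against 83.6% adjusted.
- rho 0.5: 0.495 × 0.25 + 0.75 = 0.874, power 85.1% against 89.9%.
- rho 0.7: 0.495 × 0.09 + 0.51 = 0.555, power 96.4% against 97.5%.

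The adjusted power is unchanged, because the common baseline mean cancels from the arm difference.

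**Step 5: unequal SDs.** With k = 0.8, rho = 0.5 and complete data, the free factor is 1 + 0.64 − 0.80 = 0.84. Power is 86.4% against 89.9%, a gain of 3.5 points.

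**Step 6: another scale for the effect.** If 0.555 is instead the effect on the change scale, so that the interaction itself has 80% power, the adjusted contrast at k = 1 has effect 0.555 × √(2/(1 + rho)). Its power is 93.5%, 89.9% and 86.0% at rho 0.3, 0.5 and 0.7. The direction is the same.

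**The case against.** The strongest objection is that the faulted model is nowhere written down. The plan speaks of a mixed model and of group-by-time; it does not say that baseline means are free, and the provision in Data Quality does not rule out baseline severity as a covariate. This stands in part: the model is inferred. But if baseline adjustment was intended, the text still has to say so, because it permits two models that give different intervals.

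The second objection is to the size. Taking about 10 points as the cost rests on rho = 0.5, equal SDs and complete data. The plan chose a mixed model partly because complete data are not required, and keeping dropouts' baselines roughly halves the gain at rho 0.5. Equal SDs are also not assured. Entry requires a PTSD diagnosis, which may narrow the baseline spread, and CAPS-5 is scored over the past month at baseline but the past week at follow-up. All of this stands, so the size has to be given as a range.

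A reader might also infer that the plan throws baseline information away, or that a chance baseline imbalance passes in full into each contrast. Neither follows. With complete data and equal SDs the free-baseline contrast beats follow-up alone whenever rho exceeds 0.5 (95.1% against 80.0% at rho 0.7). Given an imbalance, its expected shift is (1 − rho) times that imbalance, or half of it at rho 0.5.

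Finally, the post hoc section shows that arm results were known, so a change of model now cannot be presented as prespecified. That stands and shapes the fix.

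**Conclusion.** The point holds as an avoidable loss of precision, on the natural but inferred reading of the plan. Apart from the trivial cost of estimating the covariate slope, baseline adjustment is never less precise in expectation, and it gains whenever k differs from rho.

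For one follow-up contrast at 52 per arm and d = 0.555, with equal SDs, the gain at rho 0.3 to 0.7 runs from 17.7 down to 2.4 points with complete data. It runs from 9.4 down to 1.1 points if all 210 women are randomised and dropouts' baselines are kept. A baseline SD of 0.8 of the follow-up SD also reduces it, to 3.5 points at rho 0.5 with complete data. Rho, the SD ratio and the number randomised are assumptions; the documents give none of them.

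The documents do not support reading this as an invalid test: under randomisation the free-baseline contrast is unbiased, only less precise. Nor do they show that the model explains the lack of differences between arms reported in the post hoc section.

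**What to change.** In Statistical Analysis, state that for each continuous outcome measured at Time 1, the arm contrasts at its own post-baseline visits come from one of two models:
- a mixed model with visit, arm-by-visit at post-baseline visits only (so one common baseline mean) and unstructured covariance; or
- a model of the post-baseline visits with the Time 1 value, interacting with visit, as covariate.

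The first keeps women who have only a baseline value. Label these contrasts as specified after arm results were seen, and report them beside the original group-by-time analysis. State as well how baseline entered that original analysis.

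The cost is a paragraph of SAP text, a short change of model code and an extra set of reported contrasts. No new data or participants are needed. What cannot be recovered is prespecified status.

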## Statistical Analysis Post hoc: Equivalence Testing

### Detailed Methods:

While the original RCT was designed for inequality hypothesis testing, given the lack of differences seen between the 2 treatments (both performed well), we additionally conducted equivalence tests of means between the two treatment groups using two one-sided unequal-variance t-tests (TOST). These equivalence tests were performed using the TOSTER v.0.4.0 package for R [REFS Lakens (2017); Lakens, Scheel and Isager (2018)]. The changes from baseline to each follow-up time point were computed for each participant. These change scores were then used to perform two one-sided t-tests (TOST) between the two treatment groups to test for equivalence and reject the presence of the smallest effect size of interest (SESOI). This approach essentially checks to see if the 90% confidence interval bounds for the mean difference between the two groups are within the limits defined by the SESOI. Similar to Sloan, et.al. (2022), a margin of 10 was used as the SESOI. Sloan was only interested in one-side of the margin and performed non-inferiority tests since they assumed one treatment might be inferior to the other. However, we did not have an initial assumption that one treatment would be better than the other, so two one-sided tests or TOSTs were performed to test for equivalence within +/- 10 points. This SESOI was used for both the CAPS-5 and PCL-5 change score differences between the two treatment groups. It has also been suggested that a difference as small as 5 points for the CAPS-5 may be useful for comparing treatments for PTSD so the mean and standard deviation of all changes scores are also reported by group and time for descriptive comparisons. For clinical diagnostic comparisons, similar to Schnurr, et.al. (2022), the percentage of participants at each time point who still have PTSD are reported as well as the percentage who achieved a clinical response (reduction of CAPS-5 severity scores by 10 or more points from baseline), loss of diagnosis (CAPS-5 change  $\leq -10$ , no PTSD diagnosis and CAPS-5 severity score  $< 25$ ), as well as those who achieved remission (loss of diagnosis plus CAPS-5 score  $< 12$ ). All statistical analyses completed using SPSS version 27.0.0.0 [IBM Corp (2020)] and R version 4.1.2 [R Core Team (2021)].

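### The mixed model's handling of attrition rests on an unstated missing-at-random assumption, and with about half the sample expected to be lost no sensitivity analysis to departures from it is planned

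*Combined protocol and SAP*

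**What the plan says.** The Statistical Analysis section chooses multilevel mixed models over repeated-measures ANOVA because "MLM adjusts for attrition (missing data) over time and applies appropriate correlation structure between the time points". No missing-data mechanism is named there or elsewhere.

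The Power Analysis section gives an "estimated final sample size of 104 (52 per group) after expected levels of attrition (50% attrition from 210"). It does not say whether 210 counts consented or randomised women, or what share of outcomes will be missing at any visit.

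The Data Quality section is not silent on the subject. It says that "an assessment of missing data will be performed to check for any biases which may occur", looks at demographic and clinical factors linked to attrition, and adjusts later models for covariates found to predict missingness. It defines retention as completing every study assessment.

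The post hoc equivalence section computes each participant's change from baseline and compares the arms by two one-sided unequal-variance t-tests with a margin of 10 points either way. It describes no imputation or other treatment of missing follow-up. It also notes that "a difference as small as 5 points for the CAPS-5 may be useful for comparing treatments for PTSD".

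**The concern.** A mixed model fitted by likelihood recovers the right means when dropout depends on data that have been observed and are in the model. If women leave because of how they are doing after their last assessment, the model predicts their missing scores wrongly. The two arms are a trauma-focused therapy of twelve sessions and a yoga programme of ten. Reasons for leaving could differ between them, and that is the situation in which the between-arm comparison is biased. Covariate adjustment works only through observed data, so it cannot reveal such a process.

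The equivalence tests are more exposed. A change score exists only for a woman who has that follow-up, so these tests lack even the protection that the mixed model has under MAR. Both the finding of no difference and the equivalence statement therefore depend on an assumption that a reader cannot weigh from the planned output.

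**Working it through.** **The plan's own figure.** The documents give "we will be powered at 80% to detect moderate effect sizes for any differences between the groups" at 52 per group and d = 0.555. Alpha is not stated, so I take 0.05 two-sided. The noncentrality is 0.555 × √(52/2) = 2.83 on 102 degrees of freedom, and the noncentral t gives power of 80.05%. The planned loss is 1 − 104/210 = 50.5%. Both agree with the text, so the power statement is not in dispute.

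**Does the mixed model's validity depend on the mechanism?** I used a large-sample simulation with no true difference between arms. It had three visits, correlations of 0.5 to 0.7 and about 50% missing at the last visit in each arm (all but the last figure are assumptions). Bias in the between-arm difference from the likelihood estimate was:

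- dropout in one arm depends on the observed earlier score (MAR): 0.00 SD, against −0.29 SD if only completers are used;
- dropout in one arm depends on the unseen final score: −0.23 SD;
- the same dependence in opposite directions in the two arms: −0.45 SD;
- the same dependence in both arms: 0.00 SD.

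**Bias in points.** Let p be the share missing in an arm. Let delta be the amount by which the unseen scores are worse than the analysis implies: worse than the model's prediction for the mixed model, or worse than the mean of women with follow-up for the change-score t-tests. Then

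bias = p1 × delta1 − p2 × delta2.

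The documents give no delta, so 3, 5 and 8 points are assumptions.

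- Equal delta, 50% missing in both arms: 0.
- Equal delta in both arms, 60% v 50% missing (an assumed imbalance): 0.10 × delta = 0.3, 0.5 or 0.8 points.
- Delta in one arm only, 50% missing: 0.50 × delta = 1.5, 2.5 or 4.0 points.

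**Effect on the test of difference.** The SD is not in the documents. I assume 12, with a range of 10 to 14. SE = SD × √(2/52), which is 2.35 at SD 12, 1.96 at SD 10 and 2.75 at SD 14. With k = bias/SE, type I error = P(Z > 1.96 − k) + P(Z < −1.96 − k).

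| Bias (one arm only) | k at SD 12 | Type I error, SD 12 | SD 14 to SD 10 |
|---|---|---|---|
| 1.5 | 0.64 | 10% | 9–12% |
| 2.5 | 1.06 | 19% | 15–25% |
| 4.0 | 1.70 | 40% | 31–53% |

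For the imbalance case (0.3 to 0.8 points), type I error at SD 12 is only 5.2% to 6.3%.

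**Effect on the equivalence test.** Suppose the true difference is exactly 10 and the bias runs toward zero. Equivalence is declared if the estimate lies below 10 − 1.645 × SE, which is 6.13 at SD 12. The lower bound plays no part here. The chance of this is P(Z < (6.13 − (10 − bias))/2.35).

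| Bias | False equivalence, SD 12 | SD 14 to SD 10 | Nominal |
|---|---|---|---|
| 1.5 | 16% | 14–19% | 5% |
| 2.5 | 28% | 23–36% | 5% |
| 4.0 | 52% | 43–65% | 5% |

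These are normal approximations that treat 52 per arm as the effective size.

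**The case against.** Several points on the other side are sound.

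- In context, the sentence on attrition contrasts mixed models with an ANOVA that needs complete data, and as a contrast it is right.
- A reader might infer that the plan ignores missing data or regards it as solved. Data Quality contradicts that. Table 1 also schedules CAPS-5 and PCL-5 at mid-treatment, so worsening before a later dropout is partly observed and can inform the model.
- A reader might infer that the plan should have tested MAR. Observed data cannot distinguish MAR from its alternatives, so no such test exists. What is missing is a sensitivity analysis.
- A reader might infer that half the Time 4 outcomes will be missing. The documents do not say so. The 50% is a planning figure, some loss may come before randomisation, and a woman who misses one assessment counts as not retained yet may have Time 4 data. Bias falls in proportion: at 30% missing, a delta of 8 in one arm gives 2.4 points.
- The larger error rates need the departure to sit in one arm. The same departure with the same dropout in both arms cancels, and even 4.0 points is below the 5-point difference that the equivalence section mentions.
- The statement about mixed models does not govern the equivalence tests.

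The last point does not help the plan, because those tests have no stated missing-data method at all. The others limit the size of the concern. None supplies the missing analysis, and the documents give no reason to expect equal mechanisms in the two arms.

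**Conclusion.** The point holds in a limited form. The plan claims that the model handles attrition without giving the condition, expects to lose about half of 210, and plans nothing to show how far the conclusions depend on MAR. As described, the equivalence tests use only women with the relevant follow-up.

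The possible bias runs from zero, through 0.3 to 0.8 points for an equal shift under modest dropout imbalance, to 1.5 to 4.0 points for a shift in one arm only. These figures rest on assumed deltas, dropout shares by arm and SD. They show what a sensitivity analysis would examine and are not estimates of what happened. A reader might infer that the trial's similarity of arms is an artefact of dropout. The documents give no dropout by arm and no results by dropout status, so they do not support that.

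**What to change.** 1. In the Statistical Analysis section, replace the unqualified claim with a statement that the mixed model is valid if data are missing at random given the variables in the model.
2. Report the number of missing CAPS-5 and PCL-5 scores by arm and visit, with reasons where recorded.
3. For CAPS-5 and PCL-5 at Times 3 and 4, repeat the test of difference and the equivalence test with its 10-point margin after multiple imputation under MAR, done separately by arm and including the Time 2 scores.
4. Repeat both with the imputed values shifted over a stated grid, for example 0 to 10 points, in each arm separately and in both. The grid is a choice of range for individual scores and should be justified as such, since the plan's 10-point margin applies to a difference in means. Report the shift at which each conclusion changes.
5. Label the analysis post hoc where results are already known. If a small shift overturns a conclusion, state that conclusion as dependent on MAR.

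A pattern-mixture analysis with arm-specific shifts would serve the same purpose. The work uses existing data and needs no new participants. The cost is a little analysis time and possibly a more cautious conclusion.
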